### 1.3.1.2 Clinical experience

#### 1.3.1.2.1 Clinical safety, efficacy and tolerability

The phase I study of ceritinib demonstrated preliminary evidence of antitumor activity in *ALK*-positive NSCLC. The majority of these patients in this trial had received prior chemotherapy (median of 3 regimens) and the majority also received prior crizotinib. Among 114 response-evaluable patients with at least 18 weeks of follow-up, or who discontinued study earlier, and were treated with ceritinib doses of 400 mg daily or higher, 66 (58%) patients have responded. The response rate to ceritinib is similar regardless of prior *ALK* inhibitor therapy. In patients with NSCLC treated at  $\geq 400$  mg daily, who had previously received crizotinib, the response rate was 57%, and in those who had not previously received crizotinib it was 60%. Post-baseline tumor measurements are available for 104 of the 114 response evaluable patients. A waterfall plot displaying the maximum decrease from baseline in the sum of the longest tumor diameters (Figure 1-1) shows that the large majority of patients treated with ceritinib had a reduction in tumor burden. The median duration of response in patients who responded and were treated at  $\geq 400$  mg daily was 8.2 months (95% CI: 6.9, not estimable), and 71% had a duration of response of 6 months or longer.

After treatment with ceritinib, responses were seen in the CNS in lesions that were not treated with any other modality. The available data from the phase I study indicate that ceritinib has substantial antitumor activity in chemotherapy-treated *ALK*-positive NSCLC patients regardless of prior *ALK* inhibitor therapy.

In the Phase I trial of ceritinib [8], dose-limiting toxicities included diarrhea, vomiting, nausea, dehydration, hypophosphatemia and elevated alanine transferase. The most common adverse events included nausea (82%), diarrhea (75%), vomiting (65%), fatigue (47%), and increased alanine aminotransferase levels (21%). The common grade 3 or 4 adverse events were increased alanine aminotransferase (21%), increased aspartate aminotransferase (11%), diarrhea (7%), and increased lipase levels (7%).

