### 3.2 Inclusion criteria

Patients eligible for inclusion in this early treatment protocol have to meet **all** of the following criteria:

1. Histologically or cytologically confirmed diagnosis of lung adenocarcinoma that demonstrates *ALK* rearrangement as detected by the approved FISH test (Abbott Molecular Inc), using Vysis breakapart probes (defined as 15% or more positive tumor cells); or the Ventana IHC test. Evidence of rearrangement by gene sequencing tests such as FoundationOne or Caris will also be seen as evidence of *ALK* abnormality and meeting eligibility requirement.
2. Patients with no prior *ALK*-inhibitor therapy will be placed in cohort A, those treated with one prior line of *ALK*-inhibitor (at any time) will enter cohort B.
3. Patients will not have any other curative therapeutic option, such as radiation or surgery.
4. WHO performance status 0-2.
5. Age  $\geq$ 18 years.
6. Patients must have recovered from all toxicities related to any prior anticancer therapies to  $\leq$  Grade 2 (CTCAE v 4.03), provided that any concomitant medication is given prior to initiation of

treatment with ceritinib. Exception to this criterion: patients with any grade of alopecia are allowed to enter the treatment.

7. Adequate organ function: the following laboratory criteria have been met:
  - Absolute neutrophil count (ANC)  $\geq 1.5 \times 10^9/L$
  - Hemoglobin (Hgb)  $\geq 8$  g/dL
  - Platelets  $\geq 75 \times 10^9/L$
  - Serum creatinine  $< 1.5$  mg/dL and /or calculated creatinine clearance (using Cockcroft-Gault formula)  $\geq 30$  mL/min
  - Total bilirubin  $\leq 1.5$  x upper limit of normal (ULN), except for patients with Gilbert's syndrome who may be included if total bilirubin  $\leq 3.0$  x ULN or direct bilirubin  $\leq 1.5$  x ULN
  - Aspartate transaminase (AST)  $< 2.0$  x ULN, except for patients with liver metastasis, who are only included if AST  $< 3$  x ULN; alanine transaminase (ALT)  $< 2.0$  x ULN, except for patients with liver metastasis, who are only included if ALT  $< 3$  x ULN
  - Alkaline phosphatase (ALP)  $\leq 5.0$  x ULN
  - Fasting plasma glucose  $\leq 175$  mg/dL ( $\leq 9.8$  mmol/L)
  - Serum amylase  $\leq 2$  x ULN
  - Serum lipase  $\leq$  ULN
8. Patient must have the following laboratory values or have the following laboratory values corrected with supplements to be above the lower limit of normal before the first dose of ceritinib:
  - Potassium
  - Magnesium
  - Phosphorus

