**Table 4-3 Criteria for interruption and re-initiation of Ceritinib treatment**

Worst toxicity (CTCAE 4.03 Grade)*	Dose Modifications for Ceritinib
HEMATOLOGICAL	
Neutropenia (ANC)	
Grade 1 (ANC < LLN - $1.5 \times 10^9/L$ )	Maintain dose level
Grade 2 (ANC < 1.5 and $\geq 1.0 \times 10^9/L$ )	Maintain dose level
Grade 3 (ANC < 1.0 and $\geq 0.5 \times 10^9/L$ )	Omit dose until resolved to $\leq$ Grade 2, then: If resolved in $\leq 7$ days, then maintain dose level If resolved in $> 7$ days, then $\downarrow$ 1 dose level
Grade 4 (ANC < $0.5 \times 10^9/L$ )	Omit dose until resolved to $\leq$ Grade 2, then: If resolved in $\leq 7$ days, then maintain dose level If resolved in $> 7$ days, then $\downarrow$ 1 dose level
Febrile neutropenia (ANC < $1.0 \times 10^9/L$ , with a single temperature of $\geq 38.3$ °C or a sustained temperature of $\geq 38$ °C for more than one hour )	Omit dose until clinically resolved and neutropenia $\leq$ Grade 2, then $\downarrow$ 1 dose level

Worst toxicity (CTCAE 4.03 Grade)*	Dose Modifications for Ceritinib
Thrombocytopenia	
Grade 1 (PLT < LLN - 75 x 10  /L)	Maintain dose level
Grade 2 (PLT < 75 and ≥ 50 x 10  /L)	Maintain dose level
Grade 3 (PLT < 50 and ≥ 25 x 10  /L)	Omit dose until resolved to ≤ Grade 2, then: If resolved in ≤ 7 days, then maintain dose level If resolved in > 7 days, then ↓ 1 dose level
Grade 4 (PLT < 25 x 10  /L)	Omit dose until resolved to ≤ Grade 2, then ↓ 1 dose level
HEPATIC	
alkaline phosphatase and/or Gamma-glutamyl transpeptidase (GGT)	
Isolated elevations of any grade	Maintain dose level
Total Bilirubin** (for patients with Gilbert Syndrome these dose modifications apply to changes in direct (conjugated) bilirubin only)	
Grade 1 (> ULN and ≤ 1.5 x ULN)	Maintain dose level with liver function test (LFTs)*** monitored as per protocol
Grade 2 (> 1.5 and ≤ 3.0 x ULN) with ALT or AST ≤ 3.0 x ULN	Omit dose until resolved to ≤ Grade 1, then: If resolved in ≤ 7 days, then maintain dose level If resolved in > 7 days, then ↓ 1 dose level
Grade 3 (> 3.0 and ≤ 10.0 x ULN) with ALT or AST ≤ 3.0 x ULN	Omit dose until resolved to ≤ Grade 1, then: If resolved in ≤ 7 days, ↓ 1 dose level If resolved in > 7 days discontinue patient from ceritinib
Grade 4 (> 10.0 x ULN)	Permanently discontinue patient from ceritinib
AST or ALT	

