Grade 1 (> ULN and ≤ 3.0 x ULN)	Maintain dose level with LFTs*** monitored per protocol
Grade 2 (> 3.0 and ≤ 5.0 x ULN) without total bilirubin elevation to > 1.5 x ULN	Omit dose until resolved to ≤ Grade 1, then If resolved in ≤ 7 days, then maintain dose level If resolved in > 7 days, then ↓ 1 dose level
Grade 3 (> 5.0 and ≤ 20.0 x ULN) without total bilirubin elevation to > 1.5 x ULN	Omit dose until resolved to ≤ Grade 1, then If resolved in ≤ 7 days, then maintain dose level If resolved in > 7 days, then ↓ 1 dose level
Grade 4 (> 20.0 x ULN) without bilirubin elevation to > 2.0 x ULN	Omit dose until resolved to ≤ Grade 1, then ↓ 1 dose level
AST or ALT and concurrent Total Bilirubin	
AST or ALT > 3.0 x ULN with total bilirubin > 2.0 x ULN in the absence of cholestasis or hemolysis	Permanently discontinue patient from ceritinib

Worst toxicity (CTCAE 4.03 Grade)*	Dose Modifications for Ceritinib
RENAL	
Serum creatinine	
Grade 1 (>1 and ≤1.5 x baseline; > ULN and ≤1.5 x ULN)	Maintain dose level
Grade 2 (>1.5 and ≤3.0 x baseline; >1.5 and ≤3.0 x ULN)	Omit dose until resolved to ≤ Grade 1, then: If resolved in ≤ 7 days, then maintain dose level If resolved in > 7 days, then ↓ 1 dose level
Grade 3 (>3.0 x baseline; >3.0 and ≤6.0 x ULN)	Omit dose until resolved to ≤ Grade 1, then ↓ 1 dose level
Grade 4 (> 6.0 x ULN)	Permanently discontinue patient from ceritinib
GASTROINTESTINAL	
Diarrhea****	
Grade 1 (despite maximal anti-diarrheal medication)	Maintain dose level but adjust anti-diarrhea treatment (may change anti-diarrhea treatment)
Grade 2 (despite maximal anti-diarrheal medication)	Omit dose until resolved to ≤ Grade 1, then maintain dose level. If diarrhea returns as ≥ Grade 2, then suspend dose until resolved to ≤ Grade 1, then ↓ 1 dose level
Grade 3 (despite maximal anti-diarrheal medication)	Omit dose until resolved to ≤ Grade 1, then ↓ 1 dose level
Grade 4 (despite maximal anti-diarrheal medication)	Omit dose until resolved to ≤ Grade 1, then ↓ 1 dose level
Nausea*****	
Grade 1 (despite standard anti-emetics)	Maintain dose level but adjust anti-emetic treatment
Grade 2 (despite standard anti-emetics)	Maintain dose level but adjust anti-emetic treatment
Grade 3 (despite standard anti-emetics)	Omit dose until resolved to ≤ Grade 1, then ↓ 1 dose level
Vomiting*****	
Grade 1 (despite standard anti-emetics)	Maintain dose level but adjust anti-emetic treatment

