Grade 1 (> ULN and ≤1.5 x ULN)	Maintain dose level
Grade 2 (>1.5 - 2.0 x ULN)	Maintain dose level
Grade ≥3 (> 2.0 x ULN)	Omit dose until resolved to ≤ Grade 1, then ↓ 1 dose level
Note: Withhold ceritinib for acute onset of new or progressive unexplained abdominal symptoms, such as severe pain or vomiting; perform diagnostic procedures (e.g., abdominal CT scan or ultrasound) to exclude pancreatic pathology.	

* Common Terminology Criteria for Adverse Events (CTCAE) version 4.03. All dose modifications should be based on the worst preceding toxicity.
 
** If Grade 3 or 4 hyperbilirubinemia is due to the indirect (non-conjugated) component only, and hemolysis as the etiology has been ruled out as per institutional guidelines (e.g., review of peripheral blood smear and haptoglobin determination), then ↓ 1 dose level and continue treatment at the discretion of the Investigator.
 
***LFTs include albumin, ALT, AST, total bilirubin (fractionated if total bilirubin > 2.0 x ULN), Alkaline phosphatase and GGT.
 
**** Dose modifications apply to patients who experience diarrhea despite appropriate antidiarrheal medication. This medication should be started at the first sign of abdominal cramping, loose stools or overt diarrhea (see Section 4.3.2.5).
 
***** Dose modifications apply to patients who experience nausea and/or vomiting despite appropriate antiemetic medication. This medication should be started at the first sign of nausea and/or vomiting (see Section 4.3.2.6).
	

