#### **4.3.2.2 Guidelines for the follow-up of laboratory liver abnormalities**

In patients with any clinically relevant laboratory liver abnormality, as defined below, hepatic toxicity monitoring must include **ALL** of the following liver function tests (LFTs): albumin, ALT, AST, total bilirubin (fractionated if total bilirubin  $> 2.0 \times$  ULN), alkaline phosphatase and GGT. Note: for patients with Gilbert Syndrome, total and direct bilirubin must be monitored, but intensified monitoring applies to changes in direct bilirubin only.

In case of any occurrence of ALT/AST/total bilirubin increase to grade 2 the LFTs must be monitored weekly (or more frequently if clinically indicated) until the event resolves to  $\leq$  grade 1. Thereafter monitoring must be continued every 2 weeks (or more frequently if clinically indicated) for two additional cycles (e.g. 8 weeks). If there is no recurrence of  $\geq$  grade 2 ALT/AST/total bilirubin elevations during this period, subsequent monitoring must be performed at least every 4 weeks.

In case of any occurrence of ALT/AST/bilirubin increase to grade 3 or 4, LFTs must be monitored weekly (or more frequently if clinically indicated) until the event resolves to  $\leq$  grade 1. Thereafter monitoring must be continued every 2 weeks (or more frequently if clinically indicated) for four additional cycles (e.g. 16 weeks). If there is no recurrence of  $\geq$  grade 2 ALT/AST/total bilirubin elevations during this period, subsequent monitoring must be performed at least every 4 weeks.

Patients who discontinue ceritinib treatment due to liver toxicity must be monitored weekly (or more frequently if clinically indicated) until the event resolves to  $\leq$  grade 1 or stabilization occurs (no CTCAE grade change over 4 weeks).

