### 7.1.2 Special Warnings and Precautions for Use:

Cardiac: symptomatic bradycardia can occur with heart rate <50/min. If possible, will avoid concurrent use of agents that may cause bradycardia (eg, beta blockers, nondihydropyridine calcium channel blockers, clonidine, digoxin). Will monitor heart rate and blood pressure regularly. Dose will be held for symptomatic bradycardia.

QTc prolongation: QTc interval prolongation has occurred in clinical studies, and may be concentration-dependent. Will periodically monitor ECG and electrolytes in patients with heart failure, bradyarrhythmias, electrolyte abnormalities, or who are taking medications known to prolong the QTc interval. May require treatment interruption, dosage reduction, or discontinuation. Will permanently discontinue in patients who develop QTc interval prolongation in combination with torsades de pointes or polymorphic ventricular tachycardia or signs/symptoms of serious arrhythmia.

Gastrointestinal toxicity: Diarrhea, nausea, vomiting, or abdominal pain occurred in the majority of patients in clinical trials; over one-third of patients required dose reductions due to severe or persistent gastrointestinal toxicity. Symptomatic management will be with antiemetics and antidiarrheals.

Hepatotoxicity: Hepatotoxicity has been observed in patients treated with ceritinib in clinical trials, including ALT levels >5 times ULN in over one-quarter of patients.

Hyperglycemia: Hyperglycemia, including grade 3 and 4 toxicity, has been observed in ceritinib-treated patients. Close monitoring of blood sugars in patients with baseline random blood sugar greater than 180, with addition of insulin or other medication to correct hyperglycemia.

Pulmonary toxicity: Severe and life-threatening interstitial lung disease (ILD)/pneumonitis (some fatal) may occur. Monitor for signs/symptoms of pulmonary toxicity; permanently discontinue in patients diagnosed with treatment related ILD/pneumonitis.

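### Table 4-3's combined AST/ALT and bilirubin stopping row has no Gilbert provision, so some Gilbert patients admitted under criterion 7 meet its bilirubin condition from day 1 (minor, cheap to correct)

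*Combined protocol and SAP*

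**What the plan says.** All references are to the combined protocol and SAP.

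- **Entry (section 3.2, criterion 7).** Total bilirubin may be at most 1.5 x ULN, "except for patients with Gilbert's syndrome who may be included if total bilirubin" is at most 3.0 x ULN or direct bilirubin is at most 1.5 x ULN. AST and ALT must be below 2.0 x ULN, "except for patients with liver metastasis, who are only included if ALT" is below 3 x ULN (AST likewise).
- **Table 4-3, Total Bilirubin block.** The block heading says that "for patients with Gilbert Syndrome these dose modifications apply to changes in direct (conjugated) bilirubin only".
- **Table 4-3, AST or ALT block.** Grades 2 and 3 lead to a hold, then resumption at the same dose if resolved within 7 days, or one level lower if not. These rows apply without total bilirubin elevation to above 1.5 x ULN. Grade 4 leads to a hold and a one-level reduction, without bilirubin elevation to above 2.0 x ULN. Gilbert syndrome is not mentioned.
- **Table 4-3, combined block.** The trigger is "AST or ALT > 3.0 x ULN with total bilirubin > 2.0 x ULN in the absence of cholestasis or hemolysis" and the action is permanent discontinuation. Gilbert syndrome is not mentioned here either.
- **Table 4-3, footnote \*\*.** It is attached to the Total Bilirubin heading and begins "If Grade 3 or 4 hyperbilirubinemia is due to the indirect (non-conjugated) component only". Once hemolysis is ruled out, it prescribes a one-level reduction with continuation at the investigator's discretion.
- **Section 4.3.2.2.** For Gilbert patients, total and direct bilirubin are both monitored, but "intensified monitoring applies to changes in direct bilirubin only".

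**The concern.** The entry rule accepts a raised total bilirubin in Gilbert patients, and the Total Bilirubin block and the monitoring section look to direct bilirubin for them. The combined row goes back to total bilirubin. A value that was accepted at entry, and has not changed on treatment, then supplies half of a permanent-stop rule.

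For the patient, the difference is between a temporary hold and permanent loss of the study drug. For the analysis, section 2.0 and the endpoint table in section 9.1 count toxicity that ends treatment, and leaving the trial for other reasons, as PFS events. A stop forced this way would enter the primary endpoint in a cohort of 18 or 15.

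**Working it through.** The plan states no figure to reproduce. The check is a literal match of patients to the hepatic rows of Table 4-3, with the Gilbert note applied only where it is printed.

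**Patients compared**
- Normal: total bilirubin 0.8 x ULN.
- Gilbert: total bilirubin 2.1, 2.5 or 3.0 x ULN (same result for all three), direct bilirubin 1.0 x ULN, unchanged since entry, no cholestasis or hemolysis.

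The AST/ALT rows can be read in two ways: bilirubin above the limit in absolute terms, or bilirubin that has risen from baseline to above it.

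| ALT (x ULN) | Normal | Gilbert, absolute reading | Gilbert, rise-from-baseline reading |
|---|---|---|---|
| 2.9 | Grade 1, maintain | Grade 1, maintain | Grade 1, maintain |
| 3.1 | Grade 2, hold and resume | Permanent stop | Grade 2 row and permanent stop |
| 10 | Grade 3, hold and resume | Permanent stop | Grade 3 row and permanent stop |
| 25 | Grade 4, hold and reduce | Permanent stop | Grade 4 row and permanent stop |

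**Does another provision remove the stop?**
1. The Gilbert note is in the heading of the Total Bilirubin block. The AST/ALT and combined blocks have their own headings and do not repeat it.
2. Footnote \*\* starts at Grade 3, which is above 3.0 x ULN, so it does not reach 2.0 to 3.0 x ULN.
3. The note in section 4.3.2.2 sets monitoring frequency, not dosing.

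**Distance from entry to trigger (ALT to 3.1 x ULN)**
- Liver metastasis, entry ALT 2.9: 3.1/2.9 − 1 = 6.9%.
- No liver metastasis, entry ALT 1.9: 3.1/1.9 − 1 = 63.2%.

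**Illustrative size.** The documents give no count of Gilbert patients in this range, so 0 or 1 among the 33 is assumed. Expected forced stops = number of such patients x probability of the ALT rise.

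| Source of rate | Rate | 0 patients | 1 patient |
|---|---|---|---|
| Grade 3–4 ALT, section 7.1.4 | 15.5% | 0 | 0.16 |
| Grade 3–4 ALT, section 1.3.1.2.1 | 21% | 0 | 0.21 |
| Section 7.1.2, "including ALT levels >5 times ULN in over one-quarter of patients" (25% used) | 25% | 0 | 0.25 |

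These are not bounds. They leave out Grade 2 rises (above 3.0 to 5.0 x ULN), which also trigger the row. They also come from earlier studies, with doses up to 750 mg in section 7.1.4, so 450 mg may give fewer.

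**The case against.** **The stop is not the only instruction.** A stable Gilbert value can fairly be read as no elevation, so that the hold-and-resume row applies. Section 4.3 ties dose changes to treatment-related toxicity, which a bilirubin value accepted at entry is not. A reader might infer that every such patient must stop. The documents do not support that on the rise-from-baseline reading: two rows apply and neither has stated precedence. What remains is still a defect. Section 11.5 requires conduct exactly as approved, with prior approval of planned deviations, so the choice should not be left to inference.

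**The combined row is not a lone exception.** A reader might infer that the rest of the protocol consistently sets indirect bilirubin aside. It does not. The AST/ALT rows also lack a Gilbert clause, and footnote \*\* still cuts the dose. The direct-bilirubin principle can be shown only at entry, in the Total Bilirubin block and in monitoring.

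**The strict rule may be deliberate.** Hepatotoxicity is an adverse event of special interest (section 7.3.2), and a conservative stop is defensible. The documents give no such reason, but they also cannot show that a looser stop is safe. This stands as a reason to seek the supplier's confirmation.

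**A simple swap to direct bilirubin would do harm.** With total bilirubin above 2.0, direct above 1.5 to 2.0 and ALT above 3.0 to 20 x ULN, today's row says stop. Under a plain swap no row would apply. This objection is correct and shapes the fix.

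**Conclusion.** The point holds as a minor one. For Gilbert patients with stable total bilirubin above 2.0 and up to 3.0 x ULN and direct bilirubin at most 1.5 x ULN, Table 4-3 gives either a permanent stop or two conflicting instructions once ALT or AST exceeds 3.0 x ULN. Other patients with the same ALT and normal bilirubin hold and resume.

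This rests on the literal wording of the row and on the absence of cholestasis or hemolysis. The number affected is unknown and may be zero; 0 to 0.25 expected stops is illustrative only.

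Two wider inferences are not supported. The first is that the same holds above 3.0 x ULN, which the direct-bilirubin entry route permits: there footnote \*\* may arguably allow reduction and continuation. The second is that the trial's conclusion is at risk: at most an isolated PFS event is involved, and no sample size or analysis method changes.

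**What to change.** Add to the combined row and to the Grade 2–4 AST/ALT rows of Table 4-3:

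> *For patients with Gilbert syndrome whose total bilirubin is at most 3.0 x ULN and whose direct (conjugated) bilirubin is at most 1.5 x ULN, total bilirubin is disregarded and the AST/ALT grade rows apply; measure direct bilirubin whenever AST or ALT exceeds 3.0 x ULN. If direct bilirubin exceeds 1.5 x ULN, the rows apply as written on total bilirubin.*

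The clause is needed in both blocks. If only the combined row changed, then on the absolute reading these patients would match no row at ALT 3.1, 10 or 25 x ULN.

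With the clause in both:
- Direct bilirubin at most 1.5 x ULN: the Gilbert patient follows the same rows as the normal-bilirubin patient in the table above.
- Direct bilirubin above 1.5 and total above 2.0 x ULN: the permanent stop stays as it is now, so no new gap opens.
- Non-Gilbert patients: nothing changes. The separate gap at bilirubin above 1.5 to 2.0 with ALT or AST above 3.0 to 20 x ULN remains.

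The cost is one clause at the next amendment. No new type of test is needed, because section 4.3.2.2 already requires direct bilirubin in Gilbert patients with liver abnormalities. The downside is a slightly less strict hepatic stop in this subgroup, so the drug supplier should confirm the wording first.

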##### General guidelines for dose modifications

- For grade 1 and tolerable grade 2 treatment-related toxicities, patients are encouraged to continue at the current dose of study treatment. For intolerable grade 2 treatment-related toxicities, dosing should be interrupted until resolution to grade 1 or lower followed by dose reduction to the next dose level.
- For grade 3 or grade 4 treatment-related toxicity that is not considered by the investigator to be life-threatening, patients should interrupt study treatment until resolution to grade 1 or lower; then study treatment may continue following a dose reduction to the next dose level, if, in the opinion of the Investigator, the patient continues to experience clinical benefit. For any grade 3 or 4 treatment-related toxicity that is considered by the investigator to be life-threatening, permanently discontinue study treatment.

More detailed ceritinib dose modification guidelines are described in Section 4.3.1 respectively for selected toxicities.

All dose modifications, interruptions or discontinuations must be based on the worst preceding toxicity as graded by the NCI Clinical Toxicity Criteria version 4.03.

Patients whose treatment is interrupted or permanently discontinued due to an AE must be followed until resolution or stabilization of the event. Patients requiring interruptions greater than 1 cycle (28 days)

should be discontinued from ceritinib treatment unless the treating physician and Principle investigator agree that the patient should resume treatment.

All patients will be followed for safety until 30 days after the last dose of ceritinib.

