#### 4.3.1 Dose modification and dose delay of Ceritinib

Guidelines for dose interruptions and re-initiation of ceritinib treatment (with or without dose reduction) are described in Table 4-2. Dosing adjustment guidelines are in Table 4-3

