**Table 4-2 Dose reduction steps for ceritinib**

Ceritinib dose levels	Dose* and schedule
Starting dose level	450 mg QD continuously
Dose level - 1	300 mg QD continuously
Dose level – 2**	150 mg QD continuously

\*Dose reduction will be based on the worst preceding toxicity as per NCI-CTCAE version 4.03.

\*\*Dose reduction below 150 mg/day is not allowed. If a dose reduction below 150 mg/day is required, the patient will be permanently discontinued from ceritinib.

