Grade 2 (despite standard anti-emetics)	Omit dose until resolved to ≤ Grade 1, then maintain dose level. If vomiting returns as ≥ Grade 2, then suspend dose until resolved to ≤ Grade 1, then ↓ 1 dose level
Grade 3 (despite standard anti-emetics)	Omit dose until resolved to ≤ Grade 1, then ↓ 1 dose level
Grade 4 (despite standard anti-emetics)	Omit dose until resolved to ≤ Grade 1, then ↓ 1 dose level
METABOLIC	
Any Grade hypophosphatemia	Treatment with phosphate supplements as clinically indicated and maintain dose level
Hyperglycemia	

Worst toxicity (CTCAE 4.03 Grade)*	Dose Modifications for Ceritinib
Persistent hyperglycemia (glucose > 250 mg/dL despite optimal anti-hyperglycemic therapy)	Omit dose until hyperglycemia is adequately controlled then resume ceritinib at ↓ 1 dose level If adequate hyperglycemic control cannot be achieved with optimal medical management permanently discontinue patient from ceritinib.
GENERAL DISORDERS	
Fatigue (asthenia)	
Grade 1	Maintain dose level
Grade 2	Maintain dose level
Grade 3	If grade 3 fatigue resolves in ≤ 7 days, maintain dose level If grade 3 fatigue lasts > 7 days, omit dose until resolved to ≤ Grade 2 and then ↓ dose level
CARDIAC INVESTIGATIONS	
Electrocardiogram QT corrected (QTc) interval prolonged	
Grade 1 (QTc 450-480 ms)	Maintain dose level
Grade 2 (QTc 481-500 ms)	Maintain dose level
Grade 3 (QTc ≥ 501 ms on at least two separate ECGs)	When QTc ≥ 501 ms is identified at the site, interrupt ceritinib treatment and perform the following: Perform an analysis of serum potassium, calcium, phosphorus, and magnesium, and if below lower limit of normal, correct with supplements to within normal limits. Review concomitant medication usage for the potential to inhibit CYP3A4/5 and/or to prolong the QT-interval. Check compliance with correct dose and administration of ceritinib. Perform a repeat ECG within one hour of the first QTc of ≥ 501 ms. If QTc remains ≥ 501 ms, repeat ECG as clinically indicated, but at least once a day until the QTc returns to < 501 ms. If QTc returns to ≤ grade 1 (< 481 ms), ceritinib will be reduced by 1 dose level (i.e., 600 mg QD or lower). Repeat ECG in 24 hours, or less, as clinically indicated; continue monitoring as clinically indicated until QTc < 481 ms

Worst toxicity (CTCAE 4.03 Grade)*	Dose Modifications for Ceritinib

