	
Repeat ECGs 7 days and 14 days (and then every 21 days) after dose resumption for all patients who had therapy interrupted due to QTc ≥ 501 ms.
 
If QTc of ≥ 501 ms recurs, interrupt ceritinib treatment. If QTc returns to ≤ grade 1 (< 481 ms), ceritinib may be reduced again by 1 dose level (i.e., 450 mg QD or 300mg QD). Repeat ECGs as described above.
 
If QTc of ≥ 501 ms recurs after 2nd dose reduction for QTc prolongation, the patient must be discontinued from study.
 
QTc of >480 ms should be reported as an adverse event (AE)

Grade 4 (QTc ≥ 501 or > 60ms change from baseline and Torsades de pointes or polymorphic ventricular tachycardia or signs/symptoms of serious arrhythmia)	Permanently discontinue patient from ceritinib
PULMONARY	

Notes:
 
 
Withhold ceritinib for acute onset of new or progressive unexplained pulmonary symptoms, such as dyspnea, cough and fever and during diagnostic workup for pneumonitis/ILD.
 
During evaluation of potential grade 2, 3, and 4 pneumonitis, if an infectious etiology is confirmed (i.e., pneumonia) and pneumonitis is excluded, then consider resuming ceritinib at current dose level after the pneumonia resolves.
 
	
PNEUMONITIS	
Any Grade treatment-related ILD/pneumonitis	Permanently discontinue patient from ceritinib.
BRADYCARDIA	
Grade 1	
Omit dose until recovery to asymptomatic bradycardia or to a heart rate ≥ 60 bpm
 
Evaluate concomitant medications known to cause bradycardia and adjust the dose of ceritinib

Grade 2	
Omit dose until recovery to asymptomatic bradycardia or to a heart rate ≥ 60 bpm
 
Evaluate concomitant medications known to cause bradycardia and adjust the dose of ceritinib

Grade 3 Grade 4 (in patients taking a concomitant medication also known to cause bradycardia or a medication known to cause hypotension)	
Omit dose until recovery to asymptomatic bradycardia or to a heart rate ≥ 60 bpm
 
If the concomitant medication can be adjusted or discontinued, resume ceritinib at ↓ 1 dose level with frequent monitoring

Grade 4 (in patients who are not taking a concomitant medication also known to cause bradycardia or known to cause hypotension)	Permanently discontinue ceritinib

Worst toxicity (CTCAE 4.03 Grade)*	Dose Modifications for Ceritinib
PANCREATIC	
Amylase and/or lipase elevations (in the absence of clinical symptoms)	

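### The Grade 3 QTc row of Table 4-3 prints doses that do not fit the trial's 450/300/150 mg ladder, and the QTc entry limit is 470 ms in one place and 450 ms in another

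*Combined protocol and SAP*

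**What the plan says.** Table 4-2 defines the dose ladder: a 450 mg start, then "300 mg QD continuously", then "150 mg QD continuously". Its footnote sets the floor: "If a dose reduction below 150 mg/day is required, the patient will be permanently discontinued from ceritinib".

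The Grade 3 QTc row of Table 4-3 (501 ms or more on at least two ECGs) interrupts ceritinib. Once QTc is back below 481 ms, "ceritinib will be reduced by 1 dose level (i.e., 600 mg QD or lower". If 501 ms or more recurs and QTc again falls below 481 ms, "ceritinib may be reduced again by 1 dose level (i.e., 450 mg QD or 300mg QD". If it "recurs after 2nd dose reduction for QTc prolongation, the patient must be discontinued from study".

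Section 4.3.1 introduces the two tables by saying that interruption and re-initiation rules ("with or without dose reduction) are described in Table 4-2. Dosing adjustment guidelines are in Table 4-3"). The table titles are the other way round: Table 4-2 holds the dose reduction steps and Table 4-3 the interruption and re-initiation criteria.

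On entry, Section 3.3 (exclusion 7) excludes a Fridericia-corrected QTc above 470 ms on the screening ECG. Table 5-4, footnote b, is attached to the screening row and makes a mean baseline QTc of 450 ms or less a condition of eligibility. It names no correction formula.

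**The concern.** The QTc row is the only row of Table 4-3 that states ceritinib doses in milligrams, and those doses do not belong to this trial's ladder. Footnote a of Table 5-4 sends the clinician to this table when QTc is prolonged, so these are working instructions. The second step matters most. It applies to a patient whose QTc has reached 501 ms or more twice, and neither dose it names is a reduction for someone correctly treated at the first step. The protocol itself says QTc prolongation may depend on concentration (Section 7.1.2) and lists it as an adverse event of special interest (Section 7.3.2).

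The entry limits raise a smaller issue of the same kind. Section 5.1.4 directs eligibility review to Section 3, where only the 470 ms limit appears. A site following that route can enrol a patient whom Table 5-4 makes ineligible.

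**Working it through.** This is a reading of one table against another; no power or event calculation is involved.

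**Inputs.** Levels of 450, 300 and 150 mg, with discontinuation if less is needed (Table 4-2); no escalation (Section 4.2); printed doses of 600 mg or lower, then 450 or 300 mg (Table 4-3, Grade 3 QTc).

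**Can the printed doses be reproduced?** One level is 150 mg.
- From 450 mg: 450 − 150 = 300 mg, then 300 − 150 = 150 mg. This does not match.
- From 300 mg (already reduced for another toxicity): 150 mg, then discontinue. This does not match.
- From 750 mg: 600 mg, then 450 mg, with 300 mg the next level down. This matches.

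The printed doses therefore fit a 750–600–450–300 mg ladder. That they were carried over from a 750 mg regimen is an inference. Section 1.6 supports it by giving 750 mg as the package-insert start, as does exclusion 8, which refers to up to five capsules daily (5 × 150 = 750 mg).

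**Printed against correct dose.**

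| Situation | Current dose | Correct action | Printed dose | Printed ÷ current |
|---|---|---|---|---|
| First QTc event | 450 mg | 300 mg (−33%) | 600 mg or lower | 600/450 = 1.33 at the named dose |
| Recurrence | 300 mg | 150 mg (150/300 = 0.50) | 300 mg | 300/300 = 1.00 |
| Recurrence | 300 mg | 150 mg (0.50) | 450 mg | 450/300 = 1.50 |
| Recurrence, patient at 300 mg when the first event occurred | 150 mg | discontinue | 300 mg | 300/150 = 2.0 |
| As above | 150 mg | discontinue | 450 mg | 450/150 = 3.0 |

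At the first step, the words allowing a lower dose admit the correct 300 mg, although read alone the parenthesis would also admit staying at 450 mg. The second step has no such wording and does not name 150 mg.

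**Entry limits.** 470 − 450 = 20 ms. A QTc above 450 and up to 470 ms passes Section 3.3 and fails footnote b. The two rules may not describe the same measurement. Section 3.3 uses QTcF on the screening ECG. Footnote b uses a mean, but the screening row schedules a single ECG, and the only set of three is before dosing on Cycle 1 Day 1.

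**The case against.** The strongest reply is that the governing words are right and only the parentheses are wrong. Both sentences call for a reduction of one dose level, and levels are defined only in Table 4-2. Giving 300 or 450 mg to a patient on 300 mg is not a reduction, and 450 mg would also breach Section 4.2. For related Grade 3–4 toxicity that is not life-threatening, Section 4.3 independently says "then study treatment may continue following a dose reduction to the next dose level". The 150 mg floor rules out the two- and three-fold cases, and a further recurrence after the second reduction ends participation. All of this stands and limits the harm. It does not remove the defect: the doses are introduced by i.e., which defines rather than illustrates, and Section 4.3 defers to Section 4.3.1 for the detail. The ban on escalation does not stop a patient on 300 mg from resuming at the printed 300 mg.

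A second reply is that the event is rare. Sections 4.4.2.8 and 7.1.4 each report one patient with QTc above 500 ms, and Section 7.1.4 gives 220 patients with ECG data. If that rate carried over, 33 × 1/220 = 0.15 first events would be expected; at about 2.5%, the approximate exact 95% upper bound, 33 × 0.025 = about 0.8. The rate is not secure. The same sections disagree on increases above 60 ms (9 patients against 2), and the 1.6% quoted for 2 patients does not fit 220, since 2/220 = 0.9%. The path to a wrong second-step dose also needs recovery, recurrence and recovery again. Rarity is granted; it is no reason to leave a wrong dose in a safety table.

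On entry, the limits can both be met by applying 450 ms, and Section 4.5.2 requires the investigator to confirm all eligibility criteria before the first dose. That favours the stricter limit, but no text says that footnote b adds to Section 3.3. Fridericia is the only correction named anywhere, so the formula gap is slight; which ECG the mean refers to remains open.

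The cross-reference in Section 4.3.1 is reversed against the table titles, although Table 4-3 does also contain dose adjustments.

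**Conclusion.** The concern holds. From a 450 mg start, the two QTc reductions should be to 300 mg and then 150 mg. The plan prints 600 mg or lower and then 450 or 300 mg. The first step can still be read correctly. The second cannot: for a patient on 300 mg its named doses are a 0% or +50% change where −50% is intended. These sizes assume that the clinician uses the printed dose rather than the one-level rule, in a patient reduced correctly at the first event. The larger multiples also require overlooking the 150 mg floor.

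The entry limits differ by 20 ms as printed, and the protocol does not say which limit or ECG governs. No firm patient count can be given. This is a dosing-safety and eligibility inconsistency that should be fixed; it does not touch the endpoints, the sample size or the analysis.

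**What to change.** - In the Grade 3 QTc row of Table 4-3, replace the two parentheses with 300 mg QD and then 150 mg QD for a patient starting at 450 mg. Refer to Table 4-2, including its 150 mg floor, for patients already reduced.
- In Section 4.3.1, swap the table references so that they match the table titles.
- State one QTc limit, one correction formula and one ECG basis (the single screening ECG or the mean of three) identically in Section 3.3 and Table 5-4. Until this is settled, apply 450 ms, which satisfies both rules.

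The cost is a protocol wording amendment and a notice to site staff.
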